7.5 Interaction with Primary Healthcare Providers

All participants, at time of consent, will be asked to list their current and past (within the last 2 years) primary healthcare provider(s). Current designated providers will receive a copy of all materials sent to study participants. Thus, healthcare providers of participants randomized to the intervention arm will be mailed a print copy of the SCP with home visit results and the survivors' personalized action plan. We will directly send the SCP to providers because studies have shown that reliance on survivors alone to disseminate a copy of their SCP to their provider is problematic.^{46,55} An analysis of existing CCSS data showed that receipt of a print media intervention and fostering increased survivor-physician dialogue was associated with increasing adherence to screening.²⁶ Providers can contact the research team with

any questions regarding the SCP and action plan contents.

- Following the 1st home visit, healthcare providers designated by participants randomized to the control arm will be mailed a print copy of the home visit results only.
- Following the 2nd home visit, healthcare providers of participants on both study arms will be surveyed with regards to their self-efficacy (including self-reported knowledge) towards providing care for childhood cancer survivors. The survey will be accompanied by a cover letter, copies of clinical results (both groups), a SCP (intervention group only), and the patient's signed HIPAA authorization and Medical Record Release (if available), requesting records from the past 3 years. If the budget permits, the study will provide an upfront honorarium to providers (not exceeding \$20). Non-responding providers will receive a 2nd survey packet (inclusive of clinical results, SCP if applicable, and the signed HIPAA authorization and Medical Record Release if available) approximately a month later with an alternative cover letter. No honorarium will accompany the 2nd packet. This will be faxed to the provider's office if a fax number is available, and/or mailed. We will repeat this process two more times if no response is received after another month.

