8.8 Primary healthcare provider measurements

Following the 2nd home visit, accompanying the mailing of a copy of participant materials (intervention group: clinical results and SCP; control group: clinical results only), all designated providers will be asked to answer questions adapted from the NCI/ACS SPARCCS (see **Appendix**).⁶¹

We will also request outpatient clinical records (clinician notes, medication lists, laboratory results) spanning the study period (and up to 2 years prior to the 1st home visit) from all participants' primary healthcare providers. We will abstract records for: 1) documentation of the participant's prior cancer history and CV risk status in relation to past cancer exposures; 2) any reference to a SCP or long-term follow-up guideline; 3) any CV screening planned or undertaken [coded separately]; 4) presence of any of the three target CV risk factors as a diagnosis/problem; and 5) interventions to address any CV risk factor [coding lifestyle or drug prescription separately]. Medications will be reviewed to examine whether, among those undertreated at the 1st home visit, there is subsequent treatment intensification (e.g., going from lifestyle prescription alone to adding medication; from lower to higher drug doses; from single to multiple drugs; **Table 7**), and whether treatment intensity differs across study arms after the intervention.

Medication (class)	Low	Medium	High
Hypertension			
Lisinopril (ACE-inhibitor)	≤10	11-30	>30
Amlodipine (calcium channel blocker)	≤2.5	2.6-9.9	≥10
High cholesterol			
Simvastatin (HMG CoA reductase inhibitor)	<20	20-39	≥40
Diabetes			
Glipizide (sulfonylurea)	<10	10-19	≥20
Insulin			Any dose

Description of how the study will engage with primary healthcare providers is otherwise described in **Section 7.5**.

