13.2 Aim 2 Analytic Plan

Hypothesis: survivors randomized to the intervention will have a lower probability of having an undertreated CV risk factor compared with the control group at 1-year follow-up.

Primary analyses: We will describe baseline characteristics (including mean/median values of our target CV parameters) and proportions of underdiagnosis and undertreatment of our 3 CV risk factors. Our primary analysis will focus on the difference in the probability of having a CV risk factor undertreated after the 2nd home visit across the 2 study arms. As in Aim 1, undertreatment of hypertension, dyslipidemia, and diabetes at the 2nd home visit will be defined as blood pressure $\geq 130/80 \text{ mmHg}$, LDL ≥ 160 or triglyceride $\geq 150 \text{ mg/dL}$ (if fasting <10 hours: $\geq 200 \text{ mg/dL}$), or HbA1c $\geq 7\%$, respectively. Survivors with pre-diabetes at baseline will be undertreated at the 2nd home visit if fasting glucose $\geq 100 \text{ mg/dL}$ (non-fasting $\geq 140 \text{ mg/dL}$) or HbA1c $\geq 5.7\%$. As some survivors may contribute up to 3 outcomes (persistent hypertension, dyslipidemia, and diabetes/pre-diabetes), we will use generalized estimating equations (GEE), accounting for intra-individual correlation of the 3 outcomes, to estimate the overall intervention effect as a single parameter (3-element vector). If multiple survivors share the same primary healthcare provider (unlikely), we will apply random effects models in lieu of GEE given multiple

cluster types. Analyses will be conducted per intent-to-treat, and include all survivors with available end points.

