Post-intervention analysis: Among Aim 2 participants (and their designated healthcare provider), we will examine the differences between intervention and control groups following the 2nd home visit with respect to 1) survivor knowledge [chi-square test], 2) survivor self-efficacy [t-test or Wilcoxon rank-sum], 3) survivor-reported medication adherence [t-test or Wilcoxon rank-sum], and 4) provider-reported knowledge and self-efficacy [chi-square tests] related to the care of childhood cancer survivors. All analyses will be intent-to-treat and include all survivors and providers with available end points. Subanalyses can stratify these outcomes by initial underdiagnosis vs. undertreatment status. *We also will analyze practice changes over the 1-year intervention period using clinical records.* This includes comparing [chi-square test] whether documentation rates differ across study arms of: 1) any CV-related screening, 2) CV-related interventions [both lifestyle and drug prescriptions], and 3) treatment intensity (**Table 7** earlier). If any survivors share the same healthcare provider, we will apply bootstrap methods to account for the effects of clustering. In secondary analyses, we will determine, via logistic regression adjusting for randomization status, whether providers of survivors who remain undertreated have lower self-reported knowledge and self-efficacy related to the care of childhood cancer survivors vs. providers of survivors no longer undertreated.

Sample size: For covariates assessed at baseline in Aim 3, we will be able to detect differences $\geq 5\%$, RRs $\leq 0.8 / \geq 1.2$, and $\geq 20\%$ of 1 standard deviation (**Table 10**). Among randomized participants (240/arm) and subanalyses (e.g., analyzing undertreatment, underdiagnosis separately: $\sim 75-150$ /arm), detectable differences will be less.

Covariate frequency	Baseline* N=320:480	Post-intervention & subanalyses		
		240:240	150:150	75:75
10% (e.g., primary care provider self-efficacy towards childhood cancer survivorship care ^{27,28})	5%/17% RR 0.5/1.7	3%/20% RR 0.3/2.0	2%/22% RR 0.2/2.2	- /28% RR -/2.8
25% (e.g., MHLC self-controlling or worried typologies ⁶⁹ ; survivor anthracycline self-knowledge ⁷⁰)	17%/34% RR 0.7/1.4	15%/37% RR 0.6/1.5	12%/40% RR 0.5/1.6	8%/47% RR 0.3/1.9

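### Aim 3 provider tests make no allowance for one survivor having several responding providers, so they may be mildly anti-conservative

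*Combined protocol and SAP*

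**What the plan says.** Randomisation is 1:1 by survivor (Section 7.2), so all providers of one survivor belong to the same arm.

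On who is surveyed, Section 8.8 states that after the second home visit "all designated providers will be asked to answer questions adapted from the NCI/ACS SPARCCS". Section 2.3 speaks of all providers designated by a single participant, and the provider row of Table 3 (Section 8.0) allows a plural. Section 7.5 has participants list current and past providers, but restricts mailings to current ones.

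On the analysis, Section 13.3 tests "provider-reported knowledge and self-efficacy [chi-square tests] related to the care of childhood cancer survivors" and adds: "All analyses will be intent-to-treat and include all survivors and providers with available end points". No lead provider is named and no rule selects one response per survivor. The clustering rule is: "If any survivors share the same healthcare provider, we will apply bootstrap methods to account for the effects of clustering". Section 13.2 has a parallel rule for Aim 2, using random effects models. It is also triggered only by shared providers, a situation that section calls unlikely.

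Other wording points to one provider each. Sections 3.2 and 8.9, and the sentence in Section 13.3 that opens the post-intervention analysis, use the singular. Table 10 sizes the provider comparison at 240 per arm.

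**The concern.** An ordinary chi-square test treats each response as independent. Two providers of the same survivor share the arm, the patient and the mailed results. In the intervention arm they also share the care plan before they are surveyed. If their answers are positively correlated, the independent information is less than the number of responses suggests, and p-values come out too small. Survivors with more responding providers also carry more weight.

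The plan recognises provider clustering, but only where several survivors share one provider. If no provider is shared, no adjustment is made. If one is, the bootstrap's resampling unit is not stated: resampling survivors would also cover several providers per survivor, whereas resampling providers would not.

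At stake are the provider half of Aim 3 Hypothesis 2 (Section 3.1.3) and the secondary logistic regression in Section 13.3. That regression relates provider answers to whether the survivor remains undertreated, a survivor-level contrast, and it specifies no survivor clustering.

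**Working it through.** **1. The plan's own figure.** In Table 10 the provider row (10% base rate, 240:240) gives detectable proportions of 3% and 20%. The text of Table 10 shows no test, so I assume the Table 9 footnote applies (Fisher's exact test, 80% power, alpha 0.05) and take it as two-sided. An exact search in 0.25-point steps gives 3.25% and 19.5%, which agrees with the printed values. The table therefore treats 240 responses per arm as independent, which fits one response per survivor.

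**2. Inflation formula.** Let m be the number of responses from a survivor and ρ the within-survivor correlation.

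- Design effect: DE = 1 + ρ × (E[m²]/E[m] − 1).
- True type I error of a nominal 5% test: 2 × [1 − Φ(1.96/√DE)].
- If a fraction g of responding survivors give two responses and the rest one, then E[m] = 1 + g and E[m²] = 1 + 3g. The bracket becomes 2g/(1 + g).

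**3. From designated to responding providers.** Let a fraction f of survivors have two current providers and the rest one, each provider responding independently with probability r. Then E[m] = r(1 + f) and E[m(m − 1)] = 2fr², so the bracket is 2fr/(1 + f). The share of responding survivors giving two responses is g = fr/(1 + f − fr).

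**4. Inputs.** The documents give neither f nor ρ. I assume f = 20-30% and ρ = 0.2-0.5. The only provider participation figure is 19%, in the Hodgkin lymphoma care-plan study described in Section 2.2. I take r = 19% as the low case and assume r = 50% as the higher case, because Section 7.5 plans repeat mailings.

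**5. Results.**

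| f | r | ρ | bracket | DE | true type I error |
|---|---|---|---|---|---|
| 20% | 19% | 0.2 | 0.063 | 1.013 | 5.1% |
| 30% | 19% | 0.5 | 0.088 | 1.044 | 5.5% |
| 20% | 50% | 0.2 | 0.167 | 1.033 | 5.4% |
| 30% | 50% | 0.5 | 0.231 | 1.115 | 6.3% |
| g = 30% | – | 0.5 | 0.462 | 1.231 | 7.7% |

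For example, row four: 2 × 0.3 × 0.5/1.3 = 0.231; DE = 1 + 0.5 × 0.231 = 1.115; 1.96/√1.115 = 1.856; two-sided tail 0.0635. At 19% response, g is only 0.038/1.162 = 3.3% (f = 20%) to 0.057/1.243 = 4.6% (f = 30%). In the last row, 30% of survivors actually yield two responses, and the true standard error is √1.231 = 1.11 times the naive one.

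**6. Simulation check.** With 240 survivors per arm, a 10% base rate and 8,000 runs per scenario:

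- 20% of survivors giving two responses, ρ = 0.3: formula 6.2%, simulated chi-square 6.1%, survivor-clustered variance 5.0%.
- 50% giving two, ρ = 0.3: formula 7.4%, simulated 7.5%, clustered 4.9%.
- 50% giving two, ρ = 0: simulated 4.8%, so no inflation.

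**7. Power.** If the 240 responses per arm came in pairs with ρ = 0.3, the effective number would be 240/1.3 = 185, and the upper detectable proportion would move from 19.5% to about 21%. The loss of power is small. The main effect is on type I error.

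**The case against.** The strongest reply is that one provider per survivor was intended. The sentence defining the analysis is singular, Sections 3.2 and 8.9 agree, and 240 per arm in Table 10 fits. Section 8.8 can be read as meaning the providers of all participants, and the plural in Section 7.5 may arise only because past providers are listed too. This stands as a reason to call the wording inconsistent. It does not close the gap, because Section 2.3 and Table 3 allow several providers for one participant, Section 13.3 includes all with end points, and no rule picks one.

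A reader might infer that the standard errors are certainly too small and that type I error does exceed 5%. The documents do not support that. Inflation needs two responders from one survivor and a positive correlation. The outcome is the provider's own knowledge and self-efficacy about childhood cancer survivors in general, so the correlation could be low. The shared care plan cannot be counted as a source in both arms: under Section 7.5 and the Table 8 footnote, control providers do not receive it until after they are surveyed. Low response, as in the 19% figure, makes pairs uncommon. However, positively correlated responding within a survivor would make pairs more common than step 3 assumes.

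It is also true that a single shared provider would trigger the bootstrap. That helps only if survivors are the resampling unit, which the plan does not say.

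**Conclusion.** The point holds conditionally. As written, the plan admits several responding providers per randomised survivor and tests them as independent, with a clustering rule aimed at a different situation. Under the assumptions in the working, the true type I error is about 5.1-6.3%, and about 7.7% if 30% of survivors yield two responses with correlation 0.5. It is 5% with one responder per survivor or zero correlation. The number of providers per survivor and the correlation are assumptions; only the 19% response figure comes from the documents.

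Section 13.3 names tests for these outcomes, so the direct effect is on p-values; any intervals built the same way would be correspondingly narrow. The Aim 3 provider comparisons and the provider logistic regression are affected. A reader might extend the concern to the Aim 2 primary analysis, but that uses survivors' own measurements and is not affected. This is a minor improvement, worth making because it is nearly free.

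**What to change.** State in Section 13.3 that provider outcomes are always analysed with the survivor as a cluster, whether or not any provider is shared. Use either a bootstrap that resamples survivors or a survivor-clustered robust variance, combined with provider clustering where providers are shared. Apply the same rule to the provider logistic regression. Alternatively, prespecify one index current provider per survivor, chosen before responses are seen, and analyse only that response. In either case, reconcile the singular and plural wording in Sections 2.3, 3.2, 8.0 (Table 3), 8.8, 8.9 and 13.3.

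The cost is a sentence or two in the plan and no new data. Clustering gives slightly wider intervals; the index-provider option discards a few responses.

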Secondary analyses: In case survivors who were newly diagnosed (i.e., underdiagnosed) following their 1st home visit differ in their response to the intervention vs. those previously diagnosed but undertreated, we will examine estimates stratified by diagnosis status at the 1st home visit. For similar reasons, we also will examine estimates if pre-diabetes are excluded. In our primary model, we also will explore whether differences vary by sex, current age, time since cancer diagnosis, obese (BMI ≥ 30 kg/m²) vs. not, health insurance vs. not, and recent history of being seen in a dedicated long-term follow-up clinic for survivors vs. not. We also will explore, among intervention participants, whether action plan scores from the 4-month session are associated with differential undertreatment rates (as a single parameter). Finally, we plan to also compare across the study arms, the measured CV risk factor values from the 2nd home visit separately: 1) average systolic pressure, 2) average diastolic pressure, 3) LDL, 4) triglyceride, 5) blood glucose, and 6) HbA1c. For this subanalysis we will use linear models, adjusting for the value at the 1st home visit as a covariate.

Sample size considerations: Assuming 60% of Aim 1 participants (n=800) meet Aim 2 eligibility with a subsequent conservative 20% drop-out rate, ~380 survivors (190/arm) would have complete data. The study would be 80% powered ($\alpha=0.05$) to detect RRs ≤ 0.88 (i.e., $\geq 12\%$ reduction in the intervention vs. control group) if the prevalence of having an undertreated CV risk factor among controls after the 2nd home visit was 90% (10% reduction from baseline). If controls had an unlikely 50% reduction, we can still detect RRs ≤ 0.71 . Analyses stratified by initial underdiagnosis or undertreatment status (~75-150/arm) will be able to detect RRs ≤ 0.79 to ≤ 0.86 , respectively. Systematic reviews have reported RRs 0.6-0.8 for strategies similar our proposed interventions in the general population.^{64,65} For continuous outcomes (secondary analyses), we will be powered to detect change equaling $\sim 30\%$ of 1 standard deviation, which equates to 5 mmHg systolic blood pressure, 3 mmHg diastolic pressure, 10 mg/dL LDL, 30 mg/dL triglyceride, 10 mg/dL glucose, and 0.3% HbA1c. Differences within these ranges have been reported by others for interventions conducted in the general population.⁶⁶⁻⁶⁸

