60% (e.g., MHLC collaborating typology ⁶⁹ ; survivor radiotherapy self-knowledge ⁷⁰ ; high medication adherence ^{30,31,67,71,72})	50%/70% RR 0.8/1.2	47%/72% RR 0.8/1.2	44%/75% RR 0.7/1.3	37%/81% RR 0.6/1.3
% standard deviation (e.g., MMAS-4, ⁶⁰ survivor self-efficacy ⁵⁶)	20%	26%	33%	46%

Potential pitfalls / solutions: Self-reported medication adherence is not as accurate as data from pharmacy databases.¹⁰⁰ However, use of these databases is unlikely to be feasible even in large integrated health systems given the relative rarity of childhood cancer survivors. Given upfront randomization, any reporting biases should be similar across study arms. Should our study uncover a suggestive association with adherence, this would provide data to support the use of more expensive medication monitoring devices in a follow-up study.¹⁰⁰ We also anticipate some missing healthcare provider responses. It is possible that providers on the intervention arm who receive the SCP could be more motivated to respond (all providers will get clinically relevant results from home visits). We will closely monitor response rates for providers across the study arms, and will compare the characteristics of responding vs. non-responding providers using American Medical Association databases (physicians only) and publically available information from state licensing boards and the internet (physicians and other providers).^{28,102} In sensitivity analyses, we can examine the differences across study arms after adjustment for characteristics that appear to differ between responding and non-responding primary healthcare providers.

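### Section 13.3: the baseline detectability sentence for Aim 3 combines limits from different rows of Table 10, and the 240:240 column takes no account of the drop-out expected in section 13.2

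*Combined protocol and SAP*

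**What the plan says.** The sample-size paragraph of section 13.3 opens "For covariates assessed at baseline in Aim 3, we will be able to detect differences" of 5% or more, RRs of 0.8 or below or 1.2 or above, and 20% or more of 1 SD. It cites Table 10 and attaches no covariate frequency.

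The 320:480 column of Table 10 gives 5%/17% with RR 0.5/1.7 at 10% frequency, "17%/34% RR 0.7/1.4" at 25%, "50%/70% RR 0.8/1.2" at 60%, and 20% of 1 SD in its own row.

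The next sentence begins "Among randomized participants (240/arm) and subanalyses (e.g., analyzing undertreatment, underdiagnosis separately" and, after giving about 75-150/arm for the subanalyses, ends "detectable differences will be less".

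On who is analysed after the second home visit, section 13.3 says: "All analyses will be intent-to-treat and include all survivors and providers with available end points". Section 13.2 starts from the same 480 participants and states: "with a subsequent conservative 20% drop-out rate, ~380 survivors (190/arm) would have complete data". It gives its own subgroup sizes as "Analyses stratified by initial underdiagnosis or undertreatment status (~75-150/arm").

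Section 13.3 also expects some providers not to respond, without giving a rate.

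**The concern.** The sentence reads as a general statement of what the baseline analyses can detect. Its two limits for proportions come from opposite ends of the table: the smallest absolute difference is in the 10% row, and the RRs closest to 1 are in the 60% row. Table 10 places anthracycline self-knowledge and the self-controlling typology in the 25% row, which supports neither limit. Both belong to the first Aim 3 hypothesis.

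The post-intervention column raises a separate question. It is sized on everyone randomised, while the analysis uses only people with an end point, and the preceding section expects a fifth of participants to be lost.

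What is at stake is an accurate account of which differences Aim 3 was planned to detect.

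**Working it through.** **Inputs.** Group sizes and printed limits are from Table 10. Drop-out of 20% and 190/arm are from section 13.2. Retention of 87% in an earlier trial of care plans with telephone counselling is from section 2.2. The 40% undertreated and 80% newly diagnosed are from section 13.1. The extracted text does not show the test, alpha and power behind Table 10, so I assume two-sided 0.05 and 80%. Section 13.3 names chi-square for the proportions.

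**Formulas.** For proportions, power = Φ[(d − 1.96·s0)/s1], with s0 = √[p̄(1−p̄)(1/n1+1/n2)] and s1 = √[p1(1−p1)/n1 + p2(1−p2)/n2]. For means, the detectable fraction of 1 SD is (1.96+0.84)·√(1/n1+1/n2). Exact chi-square power was also computed. It agrees within about 1 point, except for 10% vs 3%, where it is about 2 points higher. Ranges below cover both calculations and both ways of assigning the 320 and 480.

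**Step 1: reproduce Table 10.** The 80% limits at 320:480 are 4.8/17.0%, 16.8/34.2% and 49.9/69.6%, and 2.80·√(1/320+1/480) = 0.202 SD. At 240:240 they are 3.6/19.0%, 14.8/36.8%, 47.3/72.1% and 0.256 SD. The printed values follow by rounding, except that 3/20 in the 10% row is slightly wider than chi-square requires.

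**Step 2: test the baseline sentence at 320:480.** For 25% vs 20%: p̄ = 0.22, s0 = 0.0299, s1 = 0.0303, so power = Φ[(0.05 − 0.0586)/0.0303] = Φ(−0.28) = 0.39. The other cases follow in the same way:

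| Frequency | Power, 5 points | Power, RR 0.8 or 1.2 | Limits in Table 10 |
|---|---|---|---|
| 10% | 74-77% down, 54-57% up | 14-17% | −5/+7 points, RR 0.5/1.7 |
| 25% | 34-39% | 34-39% | −8/+9 points, RR 0.7/1.4 |
| 60% | 29-30% | 92-94% | −10/+10 points, RR 0.8/1.2 |

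**Step 3: direction.** Across 320:480, 240:240, 150:150 and 75:75 the printed SD limits are 20%, 26%, 33% and 46%. Detectable differences grow as the groups shrink.

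**Step 4: sample size after drop-out.** 800 × 0.60 = 480 and 480 × 0.80 = 384, or 192/arm (about 190 in section 13.2). At 87% retention, 240 × 0.87 = 209/arm. For 25% vs 15% at 190/arm: s0 = 0.0410, s1 = 0.0407, so power = Φ[(0.10 − 0.0804)/0.0407] = Φ(0.48) = 0.68 (exact 0.69). For 26% of 1 SD: Φ(0.26·√95 − 1.96) = Φ(0.57) = 0.72. For all printed 25%, 60% and SD limits:

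| Per arm | Power of printed limits | 80% limits |
|---|---|---|
| 240 | about 78-82% | 15/37%, 47/72%, 26% SD |
| 209 | about 73-76% | 14/38%, 46/73%, 27% SD |
| 190 | about 69-72% | 14/38%, 46/73-74%, 29% SD |

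**Step 5: subgroup columns.** 0.8 × 190 = 152 and 0.4 × 190 = 76, against 0.8 × 240 = 192 and 0.4 × 240 = 96. The 150 and 75 columns therefore already appear to be net of drop-out.

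**Step 6: the 10% row.** At 190/arm the printed 3/20 has 78-82% power by chi-square but about 75% by Fisher's exact test (85-86% by Fisher at 240/arm). For providers, 10% vs 20% at assumed response rates applied to 190/arm gives 66-67% power at 75% response (143/arm) and 49% at 50% response (95/arm).

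**Step 7: the SD row.** Table 10 names both self-efficacy and MMAS-4. Section 13.3 compares MMAS-4 at baseline only among people reporting relevant medication, and section 8.1 administers it separately for blood pressure, lipid and diabetes drugs. Neither 320:480 nor 190:190 is its sample. As an illustration with assumed numbers, 100 per group gives 2.80·√(2/100) = 40% of 1 SD, and 50 per group gives 2.80·√(2/50) = 56%.

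**The case against.** Table 10 directly follows the sentence and gives every limit by frequency. A reader who consults it will not be misled for long, and the sentence could be read as quoting the best limits anywhere in the table. That reading is possible, but the sentence does not say so. The direction error may likewise be loose wording for less detectable. As written it is still backwards.

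On drop-out, 190/arm is a cautious figure. Section 13.2 itself calls the 20% conservative and ties it to complete Aim 2 data. Follow-up questionnaires come before the second home visit is arranged (section 8.7 and the Table 3 footnote), so survivor-reported outcomes may number between 190 and 240 per arm. This stands, and is why a justified higher retention is an acceptable alternative. At 209/arm the printed limits still have only 73-76% power.

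On providers, section 7.5 plans repeat mailings. Section 13.3 plans to monitor response by arm, compare responders with non-responders, and run adjusted sensitivity analyses. These address bias, not the smaller number analysed.

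It is also fair that a null result is read from its estimate and confidence interval, not from a planning limit, and that the synopsis lists Aim 3 under secondary endpoints. That limits the weight of the point. It does not make the stated figures right.

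A reader might infer more: that Table 10 is miscalculated, that every post-intervention column needs reducing, or that the trial is too small. The documents do not support this. The table reproduces, the subgroup columns already fit 190/arm, and enrolment is not derived from Aim 3.

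**Conclusion.** The point holds as a modest correction to stated planning figures. The baseline sentence claims detectability that no row of Table 10 gives: 29-39% power for 5 points at 25% or 60% frequency, and 14-17% for RR 0.8/1.2 at 10%. The statement about smaller groups is reversed. The 240:240 column overstates power for its 25%, 60% and SD limits by about 10 percentage points if 190/arm is right. In detectable size the shift is small: 1-2 points for proportions, and 26% to 29% of 1 SD.

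The 20% baseline and 27-29% follow-up SD limits can apply to self-efficacy only. MMAS-4 limits are larger, by an amount the documents do not allow one to fix. In the 10% row, whether 3/20 survives drop-out depends on the test.

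The conclusion assumes 80% power, two-sided 0.05 and chi-square. Under Fisher's exact test, which the Table 9 footnote names for Aim 1, the printed 25% and 60% limits have 75-79% power at 240/arm and 64-68% at 190/arm, so the loss is similar. The provider response rates and medication-user numbers are illustrations.

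**What to change.** 1. Replace the baseline sentence with limits by row: about 5-7 points (RR 0.5/1.7) at 10%, 8-9 points (RR 0.7/1.4) at 25%, 10 points (RR 0.8/1.2) at 60%, and 20% of 1 SD for self-efficacy.
2. Say that larger differences are needed in the smaller groups.
3. Restate the 240:240 column at 190:190 (25% vs about 14/38%, 60% vs about 46/73-74%, 29% of 1 SD). Alternatively, state a higher expected questionnaire retention and use that; at 209/arm the limits are about 14/38%, 46/73% and 27% of 1 SD. Leave the 150 and 75 columns unchanged.
4. Confine the SD limits in the baseline and restated columns to self-efficacy, and show MMAS-4 limits over a stated range of medication-user numbers.
5. Name the test used in the 10% row, and show provider outcomes over a stated range of assumed response rates.

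The cost is two reworded sentences, one restated column, and short added lines for MMAS-4 and providers. The figures become slightly less favourable. No participants are added, and enrolment and design stay as they are.
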